At the participant's last visit, the participant will be detitrated according to the following schedule:

- If at **10 mg qAM**: 5 mg qAM for 2 days, then 2 mg qAM for 2 days
- If at **15 mg qAM**: 10 mg qAM for 2 days, then 5 mg qAM for 2 days, then 2 mg qAM for 2 days
- If at **30 mg qAM**: 15 mg qAM for 2 days, then 10 mg qAM for 2 days, then 5 mg qAM for 2 days, then 2 mg qAM for 2 days

If the patient is taking strong CYP3A4 inducers, the participant's last visit, the participant will be debranded according to the following schedule:

- If at **10 mg qAM**: 4 mg qAM for 2 days
- If at **20 mg qAM**: 10 mg qAM for 2 days, then 4 mg qAM for 2 days
- If at **30 mg qAM**: 20 mg qAM for 2 days, then 10 mg qAM for 2 days, then 4 mg qAM for 2 days,

Subjects will be discontinued from the study if any of the following conditions occurs: change in diagnosis to other than bipolar I, II, or NOS disorder and AUD, development of active suicidal or homicidal ideation with plan and intent, worsening in mood symptoms, that in the opinion of the investigators requires discontinuation, pregnancy, development of severe or life-threatening medical condition, involuntary psychiatric hospitalization or incarceration, or significant alcohol withdrawal (e.g. delirium tremens) based on clinical judgment (increases in CIWA-Ar scores will initiate a careful clinical assessment of possible worsening of withdrawal symptoms).

4. Study Procedures:

Baseline: This visit will be split into two portions, Baseline 1 and Baseline 2.

For Baseline 1 (~3 hours), the psychiatric diagnoses will be confirmed by the structured clinical interview for DSM (SCID)³², mania assessed via the Young Mania Rating Scale³³ (YMRS), depression via the Hamilton Rating Scale for Depression³⁴ 17-item version (HRSD₁₇), potential withdrawal symptoms from alcohol via the Clinical Institute Withdrawal Assessment of Alcohol Use-Revised³⁵ (CIWA-Ar), recent alcohol use (and, if present, other substance use) will be assessed using the Timeline Follow Back^{29, 30} (TLFB) method, impulsivity will be assessed with the Barratt Impulsiveness Scale³⁶ (BIS-11), and blood will be drawn for complete blood count (CBC), Comprehensive Metabolic Panel (CMP, includes a liver panel with AST, ALT, as well as lipids), high-sensitivity c-reactive protein (hs-CRP), gamma glutamyl transferase (GGT), and carbohydrate-deficient transferring (CDT). If the subject elects to participate, blood will also be collected for genotyping.

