Participants will be offered an optional genetic component of their study participation and will not be prevented from participating if they choose to not contribute to this genetic component. Additional blood (20mLs) will be drawn if this component is elected. These blood samples will be sent for genotyping to UT Southwestern McDermott Center for Human Growth and Development. Genetics studies implicate the T102C HTR2A polymorphism,^{48, 49} and -1438 A/G polymorphism of the serotonin 2A (5-HT2A) receptor gene,⁵⁰ as well as the rs7916403 in serotonin receptor gene HTR7 on chromosome 10q235,⁵¹ (both receptors with affinity for aripiprazole) in alcohol dependence. Impulsivity in alcohol dependence is also associated with the -1438A polymorphism in the promoter region of the 5-HT2A receptor.⁵² The L/L genotype of the 5-HTTLPR promoter region of the serotonin re-uptake transporter (5-HTT) is associated with early onset of AUD and reduction in alcohol use with ondansetron.⁵³⁻⁵⁵ Alcohol-dependent persons homozygous or heterozygous for the seven (or longer)-repeat allele of the DRD4 VNTR responded to olanzapine with reductions in cue-elicited craving as well as alcohol consumption.⁵⁶ We will also consider adding additional genetic analyses if promising new associations should emerge (e.g. a predictor of aripiprazole response for mood symptoms), based on the available literature at the time of the analysis.

6. Criteria for Inclusion of Subjects:

- Outpatient men and women age 18-70 years old with bipolar I, II or NOS disorder, or Schizoaffective Disorder (Bipolar Type) on the SCID and confirmed by interview with a psychiatrist.
- Current diagnosis of AUD with at least moderate severity (DSM-5 terminology).
- Alcohol use (by TLFB) of an average of 15 drinks per 7 days in the past 28 days prior to intake for men and an average of 8 drinks per 7 day period in the past 28 days prior to intake for women.
- If diagnosis of: Bipolar I, Bipolar NOS with history of mania, or Schizoaffective Disorder (Bipolar Type): Current mood stabilizer therapy (lithium, valproic acid, lamotrigine, gabapentin) with stable dose for \geq 21 days prior to randomization. Patient who meet criteria for these diagnoses, but are not on mood stabilizers at the time of screening will be prescribed Lithium Carbonate (600mg daily) or Valproid Acid (500mg daily) prior to randomization, and are required to be on a stable dose for \geq 21 days before starting Aripiprazole/placebo.

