Fatigue and disturbance in attention may both be related to the sedating properties of aripiprazole. It appears to be a medication that can cause restlessness and insomnia, as well as fatigue, sedation and somnolence. These daytime side effects of aripiprazole will be managed as described above with 1) timing of study drug dosing (qHS rather than morning), and 2) adjustments in timing of concomitant medications (e.g. greater proportion of total dose in early evening than in the morning).

Finally, although not as common as the above side effects, nausea and vomiting are sometimes reported with aripiprazole. Nausea was uncommon in our pilot study (section 3.3.a) and in the aripiprazole study in alcohol dependence²⁵ but, perhaps due to the higher starting dose, was observed with greater frequency than placebo in the bipolar depression trial.⁴² We will minimize this side effect with a low-starting dose and the use of a slower dose titration when needed. If nausea is reported, the participants will be instructed to take the study drug with a meal (per package insert aripiprazole can be taken with or without food).

Please note that all side effect management will be conducted in a double-blind fashion. In all of the aripiprazole trials noted above, side effects were also reported in the placebo group. Thus, the development of side effects does not necessarily suggest that the participant is taking aripiprazole.

In order to minimize the risks related to the use of placebo, we will schedule frequent appointments with a psychiatrist investigator and research coordinator. If participants have a worsening of symptoms, such as active suicidal ideation, study participation will be discontinued, and we will provide them with referrals for appropriate care.

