All investigators and research staff will be available 24 hours a day. The consent form will have both daytime and nighttime numbers for reaching study personnel. Business cards for the research coordinator and psychiatrists will also be provided. In the event an investigator or research coordinator is on vacation or out-of-town, coverage will be provided, and both the research coordinator and UT Southwestern answering service are informed of the name and pager number of the physician-on-call. In the event of a medical or psychiatric emergency, appropriate medical advice will be provided including recommendations for emergency room evaluation if necessary. The PI and other physicians involved with the study have staff privileges at the Parkland and William P. Clements University Hospital Emergency Rooms, which are likely to be the most

commonly used hospitals by the participants. The physicians and other staff have extensive experience working with patients with bipolar disorder and substance use disorders.

All women of childbearing potential (premenopausal and without a clearly documented hysterectomy, ovariectomy or bilateral tubal ligation) must have a urine pregnancy test with negative results prior to receiving study medication. These participants will also be asked to use effective forms of contraception during the study. Pregnancy or failure to use contraceptives will result in discontinuation from the study.

Potential safety concerns will result in discontinuation from the study protocol. However, standard care will be provided until referral to another physician for further care can be arranged. The following conditions would require consideration of discontinuation from the study:

- Change in diagnosis to other than bipolar I, II, or NOS disorder and AUD.
- Development of active suicidal or homicidal ideation with plan and intent.
- Worsening in mood symptoms, that in the opinion of the investigators requires discontinuation.
- Pregnancy.
- Development of severe or life-threatening medical condition.
- Involuntary psychiatric hospitalization or incarceration.
- Significant alcohol withdrawal (e.g. delirium tremens) based on clinical judgment. Increases in CIWA-Ar scores will initiate a careful clinical assessment of possible worsening of withdrawal symptoms.

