These are general guidelines. In all cases, physician judgment will be used to determine whether or not a participant can safely remain in the study. Some level of suicidal ideation is common in the participants we research. However, we want to take steps to prevent risk of suicidal acts. Thus, the emergence of intense suicidal thoughts with a clear plan (e.g. overdose) and the intent to act on the plan would require discontinuation from the study. However, recurrent suicidal thoughts accompanied by a clear understanding that the participant does not plan to act on these thoughts would not require discontinuation.

A breathalyzer will be used to assess whether or not the participant is currently intoxicated (defined in Texas as a blood alcohol level $\geq 0.08\%$). On rare occasions, patients in our alcohol treatment studies have arrived at our clinic intoxicated. We handle this on a case-by-case basis by asking them to remain at our clinic for several hours until their blood alcohol level has decreased and, if necessary, later calling a friend to take them home. We do not allow participants to leave our clinic while intoxicated. If a patient insisted upon leaving the clinic while intoxicated, we would call campus police.

For participant safety and the internal validity of the study, concomitant medications for bipolar disorder will be managed in order to prevent discontinuation due to symptoms unrelated to the primary outcome of alcohol use, while providing consistency and structure to the medication management.

The proposed study is placebo-controlled and in a group of patients with a major mental illness and substance abuse. Given the potentially vulnerable nature of the participants, in addition to the monitoring and review by the UT Southwestern IRB, we have implemented an additional data and safety monitoring plan that includes the formation of a Data and Safety Monitoring Board (DSMB).

Adverse Events

- 1) Exclusion criteria include active suicidal ideation, pregnant or nursing women, or prisoners to minimize risk to vulnerable populations or adverse events.
- 2) All adverse events will be discussed with and evaluated by a physician investigator as soon as reported by the subject.

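### The discontinuation rules are mandatory in one section and discretionary in another, and their diagnosis wording omits an eligible diagnosis

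*Combined protocol and SAP*

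**What the plan says.** **Section 3 (Concise Summary of Project).** The list of seven conditions opens with "Subjects will be discontinued from the study if any of the following conditions occurs".

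**Section 11 (Subject Safety and Data Monitoring).** Several statements bear on the same conditions:

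- The paragraph on limiting placebo risk: "If participants have a worsening of symptoms, such as active suicidal ideation, study participation will be discontinued".
- The contraception paragraph: "Pregnancy or failure to use contraceptives will result in discontinuation from the study".
- Just before the list: "Potential safety concerns will result in discontinuation from the study protocol".
- The opening of the list, which has the same seven conditions as Section 3: "The following conditions would require consideration of discontinuation from the study".
- The first item of the list: "Change in diagnosis to other than bipolar I, II, or NOS disorder and AUD".
- The paragraph after the list, which describes the items as general guidance: "In all cases, physician judgment will be used to determine whether or not a participant can safely remain in the study". It goes on to say that intense suicidal thoughts with plan and intent require discontinuation, and that recurrent thoughts the participant does not plan to act on do not.

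**Section 6 (Criteria for Inclusion).** The eligible diagnoses are "bipolar I, II or NOS disorder, or Schizoaffective Disorder (Bipolar Type) on the SCID". The aims in Sections 1 and 14 also include the schizoaffective group.

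**Section 14 (Biostatistics, Primary Aim).** Data collection continues for participants who stop medication but stay in the study. For those who leave the study, data are analysed up to the point of leaving. Exploratory analysis 4 compares weeks in the study between arms by Cox regression.

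**The concern.** These are safety rules, and the document states no order of precedence between Section 3 and Section 11. Two clinicians who each follow the text faithfully could act differently on the same event. One rule, read literally, removes a participant whose new diagnosis would still have met the entry criteria.

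There is also a statistical consequence. Both lists discontinue the participant from the study, not only from the drug, and Section 14 treats those two outcomes differently. The rule that is followed therefore helps decide whether later TLFB data, the source of the primary outcome, exist. It also changes the duration that enters the time-in-study comparison. Some triggers, such as worsening mood or alcohol withdrawal, are plausibly related to drinking.

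**Working it through.** **Step 1. Set the rules side by side.**

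| Condition | Section 3 | Section 11 list | Elsewhere in Section 11 | Do the texts agree? |
|---|---|---|---|---|
| Change in diagnosis | Mandatory | Considered | General judgment sentence only | No |
| Severe medical illness | Mandatory | Considered | General judgment sentence only | No |
| Involuntary hospitalization or incarceration | Mandatory | Considered | General judgment sentence only | No |
| Pregnancy | Mandatory | Considered | Mandatory (contraception paragraph) | No, even within Section 11 |
| Non-use of contraception | Not listed | Not listed | Mandatory (contraception paragraph) | No |
| Suicidal ideation | Mandatory with plan and intent | Considered with plan and intent | Required with plan and intent, not required for thoughts without a plan to act (paragraph after the list); ends participation if active, with plan and intent unmentioned (placebo-risk paragraph) | Mostly, with plan and intent; not without them |
| Worsening mood | Investigator opinion | Considered, on investigator opinion | Placebo-risk paragraph: worsening symptoms end participation | The two lists nearly agree |
| Alcohol withdrawal | Clinical judgment | Considered, on clinical judgment | General judgment sentence only | Nearly |

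The first three rows are the clearest conflict: Section 3 removes the participant, Section 11 need not, and nothing else in the text settles it.

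**Step 2. Diagnosis.** Both lists name bipolar I, II or NOS disorder with AUD. Section 6 adds schizoaffective disorder, bipolar type. Take a participant enrolled with bipolar I disorder and re-diagnosed during the trial with schizoaffective disorder, bipolar type. The diagnosis has changed to one outside the listed set, so the Section 3 rule removes the participant, although the new diagnosis is eligible under Section 6.

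**Step 3. Data.** Under Section 14:

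- stops drug, stays in study: data continue to be collected;
- discontinued from study: data are analysed only up to that point.

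The lists produce the second outcome. The loss per participant runs from almost nothing (an event near week 12) to all post-baseline data (an event before the first post-baseline assessment, which also removes the participant from the ITT sample as defined).

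**Step 4. Can it be sized?** The documents give no rates for these events. Their only sample-size figure can be reproduced but does not bear on the point. With d = 0.5, two-sided alpha 0.05, 80% power and equal arms (assumed), the normal approximation gives 63 per arm. The exact t-test gives 63.8, so 64 per arm and 128 in total. Then 128 / (1 − 0.03) = 131.96, so 132. The 3% covers loss before the first post-baseline assessment only.

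Purely as an assumed range, complete loss of outcome data in a fraction f leaves 64 × (1 − f) per arm for a t-test:

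| f (assumed) | n per arm | Power |
|---|---|---|
| 0 | 64 | 80% |
| 5% | 60.8 | 78% |
| 10% | 57.6 | 76% |
| 20% | 51.2 | 71% |
| 30% | 44.8 | 65% |
| 40% | 38.4 | 58% |

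This is a worst case for losses of any cause, because the planned random regression keeps data up to discontinuation. It does not measure the effect of the conflicting rules.

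**The case against.** The best defence is that Section 3 is a summary and Section 11 is the full safety text, which tells the reader how to apply the list. That is a natural reading, and clinicians may well work that way. But the document does not say so, the Section 3 wording is unconditional, and Section 11 is itself mixed: it moves from mandatory wording to consideration to judgment within a few lines.

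Other parts of the defence stand and limit the point:

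- **Care.** A reader might infer that these events end a participant's care. They do not: Section 11 keeps standard care in place until referral or aftercare is arranged.
- **Suicidal ideation.** A reader might infer that the rule is wholly open. The paragraph after the list draws the line on both sides, and both lists use plan and intent. What remains is the broader phrase in the placebo-risk paragraph.
- **Mood worsening and withdrawal.** Section 3 already rests these on judgment, so the two lists barely differ.
- **Schizoaffective disorder.** A reader might infer that anyone enrolled with this diagnosis must be removed. The trigger is a change, so it does not reach them. The remaining case is re-diagnosis during the trial, and no visit after Baseline 1 schedules a repeat SCID.
- **Lost data.** A reader might infer that each event costs 12 weeks of outcome data, or that bias is shown. Twelve weeks is only the maximum, a multiple-imputation comparison is planned, and triggers such as pregnancy have no evident link to drinking.
- **Stopping the drug.** A reader might infer that follow-up ends when the drug stops. Section 14 already collects data from those who stay in the study. The gap lies after study discontinuation.

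**Conclusion.** The inconsistency is real and can be checked by reading the current text. The same seven conditions are mandatory in Section 3, and in Section 11 they are for consideration and then subject to judgment. The conflict is sharpest for change in diagnosis, severe medical illness, and involuntary hospitalization or incarceration. Pregnancy is handled in two ways within Section 11, contraceptive non-use is mandatory there but in neither list, and one ideation phrase is broader than the rest. The diagnosis wording does not match eligibility and could remove a participant who still has an eligible diagnosis.

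The effect on the results is a matter of direction, not size. The rule followed affects how much later TLFB data exist and the time-in-study comparison, by an amount the documents do not allow to be calculated. This conclusion assumes that study discontinuation under either list ends TLFB collection, which is how Section 14 reads. It does not show that the primary result would be biased. It supports a correction that should be made, not a challenge to the design.

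**What to change.** 1. **One list.** Reconcile Section 3 with the placebo-risk paragraph, the contraception paragraph, the list and the paragraph after it in Section 11. State for each condition, including contraceptive non-use, whether discontinuation is mandatory or judged. Which it should be is for the investigators to decide. Check the pregnancy and placebo text in Section 10 against the result.
2. **Diagnosis wording.** Make the diagnosis trigger name the same diagnoses as Section 6.
3. **A separate data rule.** Extend Section 14 so that TLFB is sought to week 12 from participants discontinued from the study, not only from study drug. This applies where they agree and contact is permissible, so not, for example, while incarcerated (Section 7 excludes incarcerated people as vulnerable). State that these data enter the ITT analysis.

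Items 1 and 2 cost a protocol wording amendment. Item 3 costs a few brief contacts. Section 4 already plans a week 18 telephone assessment that covers drinking for all participants, so remote contact of this kind is feasible.
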